11.1.2 Recording of Adverse Events

AEs/SAEs will be collected from the time the subject provides written informed consent (Screening Visit) through Period 2, Visit 9 (Month 12 ± 14 Days or ET Visit, if applicable).

Subjects will be questioned on the occurrence of an AE at every visit including any unscheduled visit, by using non-leading questioning such as 'How have you been since the last visit?'

All AEs occurring during the study observed by the Investigator or reported by the subject, whether or not attributed to study drug or the surgical procedure, will be recorded in the subject's medical records and in the eCRF. Any clinically significant changes in laboratory results or vital sign measurements (as determined by the Investigator) are to be recorded as an AE.

Ocular AEs are to be recorded on a per-eye basis.

The following information will be recorded in the eCRF for each AE: description, date of onset and end date, outcome, severity, assessment of relatedness to study drug/study procedure, the action taken and confirmation of whether the event is considered serious (see [Section 11.1.1.2](#) for the definition of seriousness). Follow-up information should be provided as necessary (see [Section 11.1.3](#) for specifics on follow-up procedures).

AE severity and relationship to the study drug or the surgical procedure will be assessed at the site by the Investigator or a medically qualified designee.

AE Severity

The severity of events will be assessed on the following scale:

- 1 = mild (awareness of sign or symptom, but easily tolerated)
- 2 = moderate (discomfort sufficient to cause interference with normal activities)
- 3 = severe (incapacitating, with inability to perform normal activities).

AE Relationship

When assigning relatedness of the AE, consideration will be given to whether there is a plausible relationship to either the study drug or the surgical procedure. The following are definitions of relatedness that will be used in this study:

Unrelated: The event is not reasonably related in time to the administration of the study drug/surgical procedure, or exposure of the study drug/surgical procedure has not yet occurred, or biologic plausibility does not exist

Related: A reasonable possibility exists that the study drug / study procedure caused the AE. A suspected AE can be further defined by:

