4.3 Definitions

Study Eye 1 (SE1) is defined as the first treated eye (within GEMINI or in an antecedent clinical trial). **Study Eye 2 (SE2)** is defined as the second treated eye (irrespective of whether the first eye was treated in GEMINI or in an antecedent clinical trial). Subjects whose first eye is treated in an antecedent study will contribute to Period 2 only (except for the immunogenicity analyses), where Study Eye 1 is the eye treated in the antecedent study and Study Eye 2 is the eye treated in GEMINI.

Period 1 starts on the day of the surgery of the first treated eye and ends on the day prior to the day of the surgery of the second treated eye. **Period 2** starts on the day of the surgery of the second treated eye.

Baseline Value of Period 1/2 is defined as the last non-missing value prior to treatment of the respective period. Baseline of each period for each eye will be used to calculate the change from baseline for the data in the same period and same eye. For example, period 1 SE1 baseline will be used to calculate the change from baseline for all the data of SE1 in period 1, whereas period 2 SE1 baseline will be used to calculate the change from baseline for all the data of SE1 in period 2.

For immunogenicity, baseline will be defined separately in [Section 4.17.11](#).

Analysis day for all the post-baseline visits will be calculated as the date of the post-baseline visits minus the corresponding injection date, depending on which baseline that was used.

For the 6 subjects whose first eye was treated in the antecedent study (Subjects [REDACTED], [REDACTED], [REDACTED]), only period 2 data are collected in GEMINI. Therefore, only period 2 data will be presented for these 6 patients.

Change from Baseline is defined as the difference of the value of an assessment at the considered visit from the baseline value of the corresponding period.

Duration is measured in days and is calculated as end date – onset date + 1.

Injection dates of SE1 and SE2 will be coded **Day 0** for the Period 1 and Period 2 respectively.

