4.17.10 Adverse Events

Treatment Emergent Adverse Events (TEAEs) are defined as AEs starting on or after the day of the first surgery. AEs reported in subjects who received timrepigene emparvovec treatment in their first eye in an antecedent study will be considered as TEAEs. Where an AE start date is partially or fully missing, and it is unclear as to whether the AE is treatment emergent, it will be assumed that it is. Summary tables will include TEAEs only. TEAEs will be summarised by eye (for ocular events), by period, and overall. Each by-period summary table will be repeated by surgery window instead.

The number and percentage of subjects reporting any event, any non-ocular event, any ocular event, any ocular event in SE1 and any ocular event in SE2 will be summarised. Percentage will be calculated based on the number of subjects in the corresponding period or surgery window or overall. The 95% CI will be calculated using the Clopper-Pearson method.

Overall summary table of TEAE by period (or by surgery window) will be provided for the following categories:

- Number and percentage of subjects with a TEAE
- Number and percentage of subjects with a serious TEAE
- Number and percentage of subjects with a Treatment-related (study drug or study procedure) TEAE
- Number and percentage of subjects with a Treatment-related (study drug or study procedure) serious TEAE
- Number and percentage of subjects with a TEAE leading to death
- Number and percentage of subjects who discontinued due to a TEAE
- Number and percentage of subjects with a TEAE by severity
- Number and percentage of subjects with a TEAE by outcome
- Number and percentage of subjects with a TEAE by action taken

Adverse events will be summarized by period (or by surgery window), and overall. The following summaries of TEAEs will be provided:

- TEAEs by SOC and PT
- TEAEs by PT with percentage $\geq 5\%$
- Treatment-related (study drug or study procedure) TEAEs by SOC and PT
- Study procedure-related TEAEs by SOC and PT
- Study drug-related TEAEs by SOC and PT
- TEAEs by SOC, PT, and maximum severity (missing severity, if any, will be counted as severe).
- Serious TEAEs by SOC and PT
- Treatment-related (study drug or study procedure) serious TEAEs by SOC and PT
- Study procedure-related serious TEAEs by SOC and PT
- Study drug-related serious TEAEs by SOC and PT
- TEAEs leading to death by SOC and PT
- TEAEs reported by subjects who discontinued due to SAE by SOC and PT

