Both counts of subjects and events will be reported. A subject with more than one occurrence of the same AE in a particular SOC will be counted only once in the total of those experiencing AEs in that particular SOC.

If a subject experiences the same AE at more than one severity, the most severe rating will be given precedence.

If a subject experiences the same AE at more than one relationship to study drug/procedure, causal relationship will be given precedence over no causal relationship. However, where a causal relationship is identified by the Investigator, the subject will be counted once within each sub-category (Study Drug, Study Procedure, Study Drug and Study Procedure, unknown).

In the summary tables, related events are defined as events that are assessed by the investigator to be related to study drug/procedure/both or with an unknown relationship.

AEs will be assigned to Period 1 or Period 2 based on the AE Start Date. An AE with a start date on or after the day of surgery of Study Eye 2 will be attributed to Period 2; otherwise, the AE will be attributed to Period 1.

An ocular event is an event where the site of the event is reported as OU, OD or OS. Where an event is recorded as 'OU', it will be counted once for each eye (SE1 and SE2).

Separate additional summaries will be provided for adverse events classified as Ocular Inflammation and Visual Acuity Reduced. The lists of PTs assigned to Ocular Inflammation and Visual Acuity Reduced are provided in a separate document (BIIB111 Signal Detection Plan). The following summaries will be provided by eye, by period (or by surgery window), and overall:

- Ocular Inflammation-related TEAEs by SOC and PT
- Ocular Inflammation-related TEAEs by SOC and PT, and by time to onset (≤ 30 days; > 30 days)
- Visual Acuity Reduced-related TEAEs by SOC and PT
- Visual Acuity Reduced-related TEAEs by SOC and PT, and by time to onset (≤ 30 days; > 30 days)

Imputation rules for partial dates are presented in Appendix 7.1.

The following listings will be provided:

- All AEs
- AEs leading to death

AEs will be coded according the MedDRA version 23.0 or higher.

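### The SAP's AE period rule puts pre-SE2 events of the six antecedent subjects in Period 1, although SAP 4.3 restricts these subjects to Period 2

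*SAP*

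**What the plan says.** Five statements bear on this point.

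- SAP 4.17.10, general definition: "Treatment Emergent Adverse Events (TEAEs) are defined as AEs starting on or after the day of the first surgery".
- SAP 4.17.10, antecedent subjects: "AEs reported in subjects who received timrepigene emparvovec treatment in their first eye in an antecedent study will be considered as TEAEs". There is no date condition.
- SAP 4.17.10, period assignment: an AE with a start date on or after SE2 surgery belongs to Period 2; "otherwise, the AE will be attributed to Period 1". There is no exception for antecedent subjects.
- SAP 4.17.10, denominators: "Percentage will be calculated based on the number of subjects in the corresponding period or surgery window or overall".
- SAP 4.3, Definitions: "Subjects whose first eye is treated in an antecedent study will contribute to Period 2 only", with immunogenicity as the only exception. Of the six subjects it adds: "Therefore, only period 2 data will be presented for these 6 patients".

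Protocol 11.1.2 fixes the start of collection: "AEs/SAEs will be collected from the time the subject provides written informed consent (Screening Visit) through Period 2, Visit 9". Antecedent subjects therefore have AEs recorded in GEMINI before their SE2 surgery. SAP 4.20, which lists changes from the protocol analyses, does not mention how these events are handled.

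**The concern.** The period rule for AEs and the period rule for antecedent subjects give different answers for the same events. An AE in one of the six subjects that starts after GEMINI consent and before SE2 surgery is a TEAE, and by its start date it falls in Period 1. By SAP 4.3 the subject is not part of Period 1. A programmer who follows 4.17.10 for the numerator and 4.3 for the denominator produces Period 1 percentages that count people outside the base. One who applies 4.3 to both must still guess what happens to these events elsewhere in the same tables.

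Safety is the study's sole objective, and the by-period TEAE summaries are core output. Period 1 describes the first exposure and Period 2 the second, so the reader will set these two columns side by side.

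**Working it through.** **Inputs**

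- Antecedent subjects: 6 (SAP 4.3 and 4.4).
- Planned enrolment: approximately 60 (SAP 3.6). I assume that 60 are treated and that the six are among them; neither is stated.
- Period 1 denominator under SAP 4.3: 60 − 6 = 54. This is inferred, since no sentence gives the Period 1 AE denominator.
- Interval: Clopper-Pearson, with the formula in SAP 4.21.

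The plan gives no figure of its own on this point, so there is none to reproduce.

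**Tracing one event.** Take an AE in an antecedent subject that starts between GEMINI consent and SE2 surgery.

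1. Collected? Yes, because collection starts at consent.
2. TEAE? Yes, by the antecedent-subject sentence in 4.17.10.
3. Period? Period 1, because it starts before SE2 surgery.
4. Is the subject in Period 1? No, by SAP 4.3.

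**Three readings.** Suppose a preferred term occurs in Period 1 in 2 of the 54 other subjects, and before SE2 surgery in 1 antecedent subject.

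| Reading | Period 1 rate | 95% CI |
|---|---|---|
| Start-date rule for the numerator, SAP 4.3 for the denominator | 3/54 = 5.6% | 1.2 to 15.4 |
| SAP 4.3 for both | 2/54 = 3.7% | 0.5 to 12.7 |
| Calendar definition of Period 1 for both | 3/60 = 5.0% | 1.0 to 13.9 |

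If the 5% cut-off for the preferred-term table is applied by column, which the SAP does not state, the term is shown under the first and third readings and not under the second.

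**Size under the first reading.** Each affected subject adds 1 to the numerator and 0 to the denominator.

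- n = 54: 1/54 = 1.9 points per subject; 6/54 = 11.1 points if all six are affected.
- n = 40 (assumed): 1/40 = 2.5 points; 6/40 = 15.0 points.
- n = 60 (assumed): 1/60 = 1.7 points; 6/60 = 10.0 points.

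An expected number of affected subjects would need an AE rate and the length of the consent-to-surgery interval. The documents give no AE rate, so I report only the range from one to six.

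**Limiting case.** If all 54 have a TEAE in Period 1, one affected antecedent subject gives 55/54 = 101.9%. The interval formula then has n − x = −1 and is undefined. This happens only when the count exceeds n.

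**Other columns.** The six are in the All Treated Subjects set (SAP 4.1), so the overall denominator already includes them. Under the second reading the events leave Period 1. If they remain TEAEs in the overall column, the event counts of the two periods no longer add up to it. The SAP does not say whether they remain there or in the surgery-window tables.

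**The case against.** The strongest reply is that SAP 4.3 already settles the matter. It is a specific rule for six identified subjects and should prevail over the generic start-date rule; their pre-SE2 events then do not appear in Period 1, and numerator and denominator match. If the calendar definition of Period 1 governs instead, the six are in both. On either consistent reading there is no mismatch. This stands in part: the mismatch is what the literal text gives, not something every programmer would produce. The conflict remains, however, because 4.17.10 has no cross-reference to 4.3, and under the 4.3 reading the place of these events in the overall and surgery-window columns is undefined. The calendar reading contradicts the Period 2 restriction. It would also add to Period 1 six people whose antecedent-study data are excluded by SAP 4.4.

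A reader might also infer that treating these AEs as treatment-emergent is an error, or that the two kinds of subject are held to different standards, since other subjects' screening AEs are left out of the TEAE tables. The documents do not support that. SAP 4.3 defines SE1 as the first treated eye, including one treated in an antecedent trial. The six subjects' GEMINI AEs therefore start after first surgery, while other subjects' screening AEs precede any exposure. The same criterion applies to both.

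Finally, the analysis is descriptive, all AEs are listed, and Protocol 7.1 moves these subjects directly into Period 2 after screening, so the interval may be short. All of this stands and limits the consequence.

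**Conclusion.** The period-assignment rule in SAP 4.17.10 conflicts with SAP 4.3 for the six antecedent subjects, and nothing in the SAP resolves it. It would go too far to conclude that the Period 1 percentages are invalid as planned: they are ambiguous, and they are wrong only if the start-date rule is applied to the numerator and SAP 4.3 to the denominator. In that case the inflation is about 1.9 points per affected subject and at most 11.1 points, assuming Period 1 n = 54; the maximum is 10 to 15 points for an assumed n of 60 down to 40. The upper bound requires all six to have an AE before SE2 surgery. The overall denominator is sound. The effect is modest, but it falls on the main tables of a safety study and is easily removed.

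**What to change.** Change the period-assignment rule and leave the TEAE definition alone. Restricting TEAEs in these subjects to events from SE2 surgery onward would drop post-exposure events from the overall column, while the same kind of event between the two surgeries would still count for subjects treated twice in GEMINI.

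Add to 4.17.10, in substance: *For subjects whose first eye was treated in an antecedent study, AEs starting before SE2 surgery are not attributed to Period 1, and these subjects are not in the Period 1 denominator. Such AEs are shown in a separate category (antecedent subjects, before SE2 surgery) with a denominator of 6, and are kept in the overall column.* State explicitly whether the surgery-window columns also keep them. Footnote the by-period tables to say that the period columns do not sum to overall.

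The cost is a short SAP addition, one extra table category and a footnote. It needs no new data and no protocol amendment.

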7 INVESTIGATIONAL PLAN

7.1 Overall Study Design

This is a multi-centre, open-label, prospective, 2-period, bilateral interventional safety study of AAV2-REP1 in adult male subjects with genetically confirmed CHM. The study will consist of a Screening Period followed by 2 treatment periods (Period 1 and Period 2) with up to 9 visits per treatment period. A second baseline visit prior to surgery of SE2 (Period 2, Visit 1) may be required. A study schematic is presented in **Figure 1**.

Figure 1 Overall Study Schematic

During the Screening Period, subjects will be assessed for eligibility of both eyes. The Investigator will assign the order in which the eyes are treated (i.e., study eye 1 [SE1]-Period 1 and study eye 2 [SE2]-Period 2, respectively) with a number assigned to each eye. This will be done in collaboration with the subject; however, the worse eye will generally be selected for first treatment. Study eye selection and eligibility for surgery will then be confirmed collectively by the Patient Eligibility Review Committee, which includes the Investigator, a consulting surgeon, and the Sponsor (see the Patient Eligibility Review Plan). The estimated target interval between the surgical procedures of SE1 and SE2 will be determined at the Screening Visit.

Each study eye will be followed for at least 12 months post-treatment, for up to 9 visits per treatment period: Visit 1 (Day 0, Injection Day Visit); Visit 2 (Day 1, post-operative follow-up visit); Visit 3 (Day 3 + 2 Days); Visit 4 (Day 7 -1/+2 Days); Visit 5 (Day 14 ± 3 Days); Visit 6 (Month 1 ± 7 Days); Visit 7 (Month 3 ± 14 Days); Visit 8 (Month 6 ± 14 Days) and Visit 9 (Month 12 ± 14 Days; end of study visit).

At Period 1, Visit 1 (Day 0, Injection Day Visit for SE1), subjects will undergo a vitrectomy with retinal detachment and receive a sub-retinal injection of AAV2-REP1 in SE1. Visits 2-9 will then be conducted according to the Schedule of Study Procedures, unless Period 2 commences during the time of follow-up for SE; in which case, the study visits will continue following the schedule for SE2. Ophthalmic assessments during Period 1, Visits 2-9 will be performed on both eyes.

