4.4 Data of Subjects with First Eye Treated in an Antecedent Study

For the 6 subjects who received timrepigene emparvovec treatment in their first eye in an antecedent study, the data from the antecedent study will not be included in the analyses presented in the Clinical Study Report (CSR).

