4.7 Subgroup Analysis

Demographic and baseline characteristics will be summarised by Surgery Site. The efficacy endpoints of BCVA will be summarised by the subgroups defined in [Table 1](#).

Table 1 Subgroups Defined at Baseline

	Values
Age 1	≤ 50 years old > 50 years old
Age 2	≤ 60 years old > 60 years old
Age 3	\leq median age $>$ median age
Race	White Non-white (American Indian or Alaska Native, Asian, Black or African American, Native Hawaiian or Other Pacific Islander)
Region	America Europe
Surgery Site	Each of the surgery sites
Surgery Window	Short [< 6 months], Medium [$6-12$ months] Long [>12 months] Overall

In addition, TEAE will also be summarized by Surgery Window (Short [< 6 months], Medium [$6-12$ months] and Long [>12 months]) and all surgery windows combined.

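### By-window adverse event percentages in SAP 4.17.10 mix the interval between surgeries with length of follow-up and, for six subjects, with one surgery instead of two

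*SAP*

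**What the plan says.** SAP 4.7 states that "TEAE will also be summarized by Surgery Window". SAP 4.17.10 then says of the by-period tables: "Each by-period summary table will be repeated by surgery window instead". Window therefore takes the place of period and is not crossed with it. TEAEs "are defined as AEs starting on or after the day of the first surgery", and Protocol 11.1.2 fixes the other end: "AEs/SAEs will be collected from the time the subject provides written informed consent (Screening Visit) through Period 2, Visit 9", or the early termination visit.

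On the denominator, SAP 4.17.10 says: "Percentage will be calculated based on the number of subjects in the corresponding period or surgery window or overall". The intervals are Clopper-Pearson. SAP 4.15 plans no evaluation of exposure, and no follow-up-time row or common at-risk period is described for these tables.

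Protocol 7.1 states: "Each study eye will be followed for at least 12 months post-treatment, for up to 9 visits per treatment period". It plans about 20 subjects in each of three windows: under 6, 6 to 12 and over 12 months between eyes.

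Six subjects had their first eye treated in an antecedent study. SAP 4.3 says "only period 2 data will be presented for these 6 patients", and SAP 4.4 keeps their antecedent data out of the study report. SAP 4.17.10 nevertheless counts their GEMINI events as TEAEs, so they are in the tables.

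**The concern.** Protocol 7.1 varies the interval in order to characterise the safety of sequential treatment. The by-window TEAE tables are the general adverse event display on that question, and they will be read across their columns.

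The grouping variable is itself a component of follow-up time: a longer interval means longer observation. The antecedent subjects break that pattern the other way, with less time and one surgery. A difference between columns can therefore arise from time at risk or from number of surgeries. The confidence limits express sampling error only and give no warning of this.

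**Working it through.** **The plan's own figures.** 3 windows × 20 = 60 subjects, and 60 × 2 = 120 eyes. Both agree with SAP 3.6. The documents give no event rate or follow-up time by window, so the event risks, the exact intervals and the placement of the antecedent subjects below are assumptions.

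**Step 1: observed time.** First surgery to Period 2 Month 12 = interval + about 12 months. Short: under 6 + 12 = under 18. Medium: 18 to 24. Long: over 24. Antecedent subjects: about 12.

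**Step 2: background events.** Here the second surgery adds no risk. Take a 12-month risk p = 20%, H = -ln(1 - p) = 0.2231, and intervals of 3, 9 and 18 months (15, 21 and 30 months observed). Incidence = 1 - exp(-H × months/12):

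- Short: 1 - exp(-0.2231 × 15/12) = 24.3%
- Medium: 1 - exp(-0.2231 × 21/12) = 32.3%
- Long: 1 - exp(-0.2231 × 30/12) = 42.8%

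The long/short ratio is 1.76. It is 1.94 at p = 5.1%, 1.42 at 50%, 1.13 at 80% and 1.02 at 95%, so near-universal events hardly move. (The 5.1% is the 4/79 in Protocol 5.4, used only as an assumed risk.)

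**Step 3: purely peri-operative events.** At 20% per surgery, two surgeries give 1 - 0.8² = 36.0% in every window, whatever the follow-up.

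**Step 4: between the two.** Let a share s of H fall in the month after each surgery, with the rest at a steady rate of (1 - s)H/11 per month. Then C = 2sH + (1 - s)(H/11)(interval + 10), and incidence = 1 - exp(-C).

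**Step 5: antecedent subjects.** If six of 20 in the long column contribute 20% each, the column is (14 × long + 6 × 20%)/20. For peri-operative events this is (14 × 36.0 + 6 × 20)/20 = 31.2%.

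| Event type | Short | Medium | Long | Long with six antecedent |
|---|---|---|---|---|
| Background only | 24.3% | 32.3% | 42.8% | 35.9% |
| s = 50% | 29.9% | 34.0% | 39.8% | 33.8% |
| s = 80% | 33.6% | 35.2% | 37.5% | 32.3% |
| s = 100% | 36.0% | 36.0% | 36.0% | 31.2% |

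With no interval effect at all, the columns can rise, stay level or fall.

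**Step 6: candidate corrections.**

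- *Pooled person-time rates.* For purely peri-operative events the rate is 1200 × 2H/(interval + 12), or 35.7, 25.5 and 17.9 per 100 person-years. That is a false fall.
- *Per-subject Period 2, 0-12 months.* If each surgery's 20% risk is spread evenly over its own 12 months, a subject with a 3-month interval enters Period 2 with 9 months of first-surgery risk left, and one with a 9-month interval with 3 months. The results are 1 - exp(-1.75H) = 32.3%, 1 - exp(-1.25H) = 24.3% and 1 - exp(-H) = 20.0%. This is another false fall.
- *Per eye, 0-12 months from that eye's own surgery.* 1 - exp(-H) = 20.0% in every window.

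**The case against.** The strongest reply has five parts.

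1. **The tables are descriptive.** SAP 4.2 rules out formal comparison, and with about 20 subjects per window the limits are wide: 5/20 gives 8.7-49.1% and 9/20 gives 23.1-68.5%. This stands. The issue is how the table is read, not a faulty test.

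2. **The background illustration overstates the effect for surgery-related events.** This also stands. The 24.3/32.3/42.8% series gives the second surgery no added risk, so it must not be read as identical risk after each surgery. If each treated eye carried its own constant hazard without limit, incidence would be 1 - exp(-H × (interval + 24)/12) = 39.5/45.9/54.2%, a ratio of 1.37. If the risk ended within 12 months of each surgery, it would be 36.0% throughout. Protocol 7.2 regards 12 months as long enough to see treatment-related concerns, so follow-up distorts the related rows less than the non-ocular or late-onset ones.

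3. **Existing analyses already help.** SAP 4.17.10 splits ocular inflammation and visual acuity reduced events at 30 days, by eye and window, in the All Treated set. SAP 4.17.11.4 crosses period with window for three event groups by assay status, and visual acuity is shown by visit and window. The SE2 row covers one surgery and about 12 months of treated follow-up for everyone; only events in the still-untreated eye before its surgery vary with the interval. All this is true, but the general, serious, related and non-ocular tables have no equal-horizon view by window.

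4. **The antecedent subjects' window can be inferred.** SAP 3.1 defines the window by the two treatments, and SAP 4.3 counts an antecedent eye as SE1. That is a reasonable reading, but the SAP does not state it or give the number per column.

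5. **Equal horizons do not isolate an interval effect.** Intervals are set case by case, and Protocol 7.1 lets the SE1 outcome inform scheduling. That confounding remains after any re-tabulation.

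**Conclusion.** The concern holds for events that accrue over time, notably in the SE1 ocular and non-ocular rows. Under equal risk the planned percentage can rise from 24.3% to 42.8% across windows, given an assumed 20% background risk and intervals of 3, 9 and 18 months. Peri-operative percentages are unaffected by follow-up, but a column with six antecedent subjects of 20 would drop from 36.0% to 31.2%. The unequal follow-up and the single surgery come from the documents; the sizes rest on the stated assumptions.

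A reader might infer more than this, and the documents do not support it:

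- *The long window is bound to look worse.* The sign depends on the type of event and on where the antecedent subjects fall.
- *The six are all in the long window.* No document says so.
- *Every row is distorted.* Peri-operative and near-universal events barely move with follow-up, and the SE2 row is touched only through the pre-surgery eye.
- *Dividing by person-time would cure it.* Pooled rates can show a false fall.

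**What to change.** Keep the planned tables and add, by surgery window:

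- **(a) Ocular TEAEs, including serious and related ones:** per eye, over 0-30 days and 0-12 months from that eye's own surgery.
- **(b) Non-ocular TEAEs, including serious and related ones:** per subject, over 0-30 days after each surgery, by period, censored at the second surgery or early termination.
- **(c) Column information:** a follow-up-time row and the number of antecedent subjects, with the rule that places them in a window. In (a) and (b) they contribute SE2 and Period 2 only.

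State that the 30-day onset split in SAP 4.17.10 starts at the surgery of the eye concerned; the section does not now name the starting surgery.

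If a per-subject Period 2 figure over 0-12 months is shown, footnote that short- and medium-window subjects may still carry first-surgery risk, so that a fall across windows is not by itself an interval effect. Do not use pooled person-time rates as the correction. Footnote also that intervals were not randomised and that SE1 outcome informed scheduling.

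The cost is SAP wording and programming from surgery, event and last-contact dates already collected, with no change to conduct. The downside is a few more tables with about 20 subjects per window and wide intervals.
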